12.2.3 Cardiopulmonary Complications

Current modified PDAY scores for AMP Up participants will be calculated using measured values of HDL cholesterol, non-HDL cholesterol, smoking status, blood pressure, obesity status ($BMI > 30 \text{ kg/m}^2$), and hyperglycemia status (defined as fasting plasma glucose $\geq 126 \text{ mg/dl}$, or a diagnosis of diabetes or report of diabetes medication). Both the coronary artery score and the abdominal aorta score will be calculated as described previously to reflect risk of atherosclerotic lesions in the coronary artery and abdominal aorta, respectively. The “modified” PDAY scores incorporate only those risk factors which are considered modifiable (e.g., exclude sex, age, and race), although the non-modifiable factors may also be strong predictors of CVD risk. All AMP Up participants with available measurements of these risk factors will be included (e.g., not restricted to the PHACS Cardiac Toxicity Substudy participants). The distribution of modified PDAY risk scores will be compared by HIV status using a Wilcoxon rank sum test. Depending on observed distributions of coronary artery and abdominal aorta scores, the outcomes may be dichotomized as higher vs. lower scores, and then compared as estimated probabilities of higher score using logistic regression models adjusted for age. The association of PDAY scores with neurocognitive function measures from the NIH Toolbox will be evaluated using GEE approaches to improve robustness, with the risk scores as the predictors and the neurocognitive outcomes as the response. If sufficient numbers of AMP Up participants have repeated measurements of cholesterol, other risk factors, and neurocognitive assessments, linear mixed models will be fit for the repeated neurocognitive outcomes as a function of current and past PDAY scores. Because not all AMP Up participants may have cholesterol and other risk factors, as well as neurocognitive measures available, inverse probability weighting approaches will be employed to account for potential selection bias. The association of cardiac and inflammatory biomarkers with neurocognitive function will be restricted to those in the Cardiac Toxicity Substudy who have these measurements obtained during AMP Up (target

120 YAPHIV, 80 YAPHEU); GEE models will be used to evaluate the associations with neurocognitive outcomes from the NIH Toolbox overall and by HIV status, adjusting for age, sex, and other potential confounders.

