2.2.2 Metabolic Complications

Specific Aim:

- To evaluate longitudinal changes in parameters of cardiometabolic risk by HIV status (YAPHIV vs. YAPHEU), including body weight and composition, lipid levels, insulin sensitivity, blood pressure, and modified PDAY scores (a predictor of atherosclerosis).
- Among YAPHIV, to evaluate the association of ART switches with changes in body weight and composition, lipid levels, insulin sensitivity, and blood pressure.
- To evaluate food security and diet in YAPHIV and YAPHEU and their associations with body composition and metabolic outcomes. Among YAPHIV, to evaluate the association of food

security with adherence to ART and whether the association is mediated through engagement in clinical care.

Hypotheses:

- YAPHIV will manifest parameters of increased cardiometabolic risk, with unfavorable trajectories compared to YAPHEU.
- Switching to newer-line ART will result in improvement in some but not all parameters of cardiometabolic risk.
- YAPHIV will have greater food insecurity than YAPHEU, and YAPHIV with food insecurity will be more likely to be obese, have poorer metabolic outcomes, and be less likely to engage in clinical care.
- YAPHIV with food insecurity will have poorer adherence to ART medications that is mediated through engagement in care.

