2.2.3 Cardiopulmonary Complications

Specific Aims:

- To evaluate the distribution of PDAY scores for YAPHIV and YAPHEU and compare the distributions by HIV status, and to assess the association of PDAY scores and cardiac biomarkers with neurocognitive function as reflected by NIH Toolbox measures.
- To determine the association between pulmonary function and left and right ventricular structure and function.
- To determine the prevalence of marijuana and nicotine vaping in YAPHIV and YAPHEU and evaluate associations of vaping with presence of asthma, pulmonary disease, and hospitalization by PHIV status.

Hypotheses:

- YAPHIV will have increased modified PDAY scores as compared to YAPHEU, which will be inversely associated with neurocognitive function. Both past and recent cardiac and inflammatory biomarkers will be inversely associated with neurocognitive function.
- Pulmonary obstructive and/or restrictive disease will be associated with left and right ventricular diastolic dysfunction, global cardiac strain, increased pulmonary artery pressure, and pulmonary vascular resistance.
- Prevalence of vaping will be similar among YAPHIV and YAPHEU, yet the presence of asthma, pulmonary disease, and hospitalization will be more pronounced among YAPHIV.

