Systolic and diastolic blood pressure, lipid levels (total cholesterol, HDL cholesterol, LDL cholesterol, and triglycerides), HOMA-IR, and cardiometabolic risk (as measured by PDAY scores) will be considered as continuous outcomes. The body composition measures (waist, mid-upper arm and hip

circumferences, and triceps, biceps, suprailiac, and subscapular skinfolds), and sum of skinfolds will be considered only as continuous outcomes. BMI will be evaluated as a binary or continuous variable.

For cross-sectional data, outcomes in YAPHIV and YAPHEU will be compared using generalized estimating equations for a continuous outcome with the robust variance estimator. Potential confounders that may be included in the models of blood pressure and lipids are BMI, sex, race, physical activity, tobacco use, and diet. Models of body composition may include all of these, but not BMI. Models of cardiometabolic risk (PDAY scores) will include age and sex. The association of each class and type of ART for each outcome in models restricted to YAPHIV will be investigated.

To examine the effect of exposures that vary over time, such as ART regimens (in YAPHIV) or body composition, mixed effects models will be used, which will account for the correlations between these repeated measures. The change over time in waist and mid-upper arm circumferences, waist-to-height ratio, triceps, biceps, suprailiac, and subscapular skinfolds, and BMI will be compared by HIV status.

To examine trajectories of the continuous outcomes between YAPHIV and YAPHEU or within YAPHIV by HIV-associated exposures such ART regimens or CD4 count, mixed effect models will be fit, adjusting for potential confounders.

The food security score will be calculated and YAPHIV and YAPHEU will be categorized into levels of food security. The association of sociodemographic factors and dietary factors with food security level will be examined using chi-square or Wilcoxon tests. In longitudinal analysis, the effect of low food security on change in BMI, lipid concentration and HOMA-IR and on adherence to ART will be evaluated. Mediation analysis will be used to examine whether an association of food security with adherence is mediated through engagement in clinical care.

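### Sections 12.2.2 and 12.2.3 adjust the same cohort comparison of modified PDAY scores differently: for age and sex in one, and for age or nothing in the other

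*Protocol*

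**What the plan says.** Both domains address the same score and the same contrast. The metabolic aims in Section 2.2.2 list modified PDAY scores among the parameters to be compared by HIV status. The cardiopulmonary hypothesis in Section 2.2.3 is that "YAPHIV will have increased modified PDAY scores as compared to YAPHEU".

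The analysis is then described twice.

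- **Section 12.2.2 (Metabolic).** The score is numeric: "and cardiometabolic risk (as measured by PDAY scores) will be considered as continuous outcomes". For cross-sectional data, "outcomes in YAPHIV and YAPHEU will be compared using generalized estimating equations for a continuous outcome with the robust variance estimator". The covariates are fixed: "Models of cardiometabolic risk (PDAY scores) will include age and sex".
- **Section 12.2.3 (Cardiopulmonary).** "The distribution of modified PDAY risk scores will be compared by HIV status using a Wilcoxon rank sum test". A further step is left open until the score distributions have been seen: "the outcomes may be dichotomized as higher vs. lower scores". If that step is taken, the model for the split scores is described in these words: "and then compared as estimated probabilities of higher score using logistic regression models adjusted for age".

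Section 12.2.3 also explains that the modified score keeps only modifiable risk factors. Sex, age and race are left out, and the section concedes that these may themselves predict cardiovascular risk strongly.

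**The concern.** This is a non-randomised contrast, so the adjustment set determines what the estimate means. The protocol fixes one set in Section 12.2.2 and a smaller one in Section 12.2.3, and gives no reason for the difference. Two reports that both follow the protocol could then reach different answers on whether YAPHIV have higher PDAY scores. The one written from Section 12.2.3 would leave any difference in sex mix between the cohorts inside the apparent HIV effect.

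**Working it through.** The plan states no figure to reproduce here. The check is a comparison of the two sections.

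| | Section 12.2.2 | Section 12.2.3 |
|---|---|---|
| Outcome | PDAY score | Modified PDAY score (coronary artery and abdominal aorta) |
| Contrast | YAPHIV vs YAPHEU | YAPHIV vs YAPHEU |
| Scale | Continuous | Ranks; possibly higher vs lower |
| Method | GEE, robust variance | Wilcoxon; logistic if dichotomized |
| Covariates | Age and sex, firmly stated | None (Wilcoxon); age (logistic) |

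1. **Is it the same outcome?** Yes. Sections 2.2.2 and 2.2.3 both name the modified score and the same two cohorts.

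2. **Does Section 12.2.2 really make a cohort comparison of PDAY?** Yes. It rules out estimating incidence of cardiometabolic risk in YAPHEU, because repeat lipid and HOMA-IR measures are lacking, but the cross-sectional comparison of the two cohorts remains. Models restricted to YAPHIV are mentioned separately.

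3. **Is the Section 12.2.2 covariate statement firm?** Yes. PDAY models will include age and sex, whereas the covariates listed for blood pressure, lipids and body composition are ones that may be included.

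4. **Is the absence of sex in Section 12.2.3 likely to be shorthand?** Probably not. The last sentence of that section, on cardiac and inflammatory biomarkers and neurocognition, names age, sex and other potential confounders.

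5. **Is an adjusted comparison guaranteed in Section 12.2.3?** No. The logistic model is fitted only if the scores are dichotomized, which is optional. Otherwise the Wilcoxon test is the section's only cohort comparison of PDAY.

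6. **Can sex matter?** On the protocol's own account, yes. Section 12.2.2 lists sex as a potential confounder for blood pressure and lipids. Section 12.2.3 builds the score from HDL and non-HDL cholesterol and blood pressure, with smoking, obesity and hyperglycemia. Removing sex as a scored item does not remove its influence through those components.

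7. **Does the design balance sex?** Nothing requires it. Sections 4.1 and 4.2 set a minimum age of 18 and no condition on sex. Section 3.0 expects a similar age distribution and well-matched groups, and Section 12.0 says only that the comparison cohort would ideally come from the same population.

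8. **How large could the effect be?** The bias is the between-cohort difference in the proportion female multiplied by the sex difference in the score. The protocol supplies neither factor, so no value follows.

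**The case against.** The strongest reply is that the two analyses are complementary. One models the mean of a continuous score. The other compares distributions, which is what the Section 2.2.3 aim asks for. A crude test followed by an adjusted model is also the protocol's usual pattern: Sections 12.2.5 and 12.2.8 label their chi-square tests as crude, and Section 12.2.10 follows a Wilcoxon test with unadjusted and adjusted models. This stands as far as the methods go, and there is no fault in having both a GEE and a rank test. It does not reconcile the covariate sets, and Section 12.2.3 departs from the pattern by neither labelling the Wilcoxon test as crude nor guaranteeing an adjusted model.

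It can also be said that covariate lists belong in the statistical analysis plan, which is not shown. That would answer a complaint of missing detail. Here the protocol has already written down two different sets for one comparison.

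Three stronger readings are tempting and should not be drawn.

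- **That any age or sex imbalance will be read as an HIV effect.** The Section 12.2.2 GEE adjusts the same contrast for both, and the logistic model adjusts for age. Only the Wilcoxon test is wholly unadjusted.
- **That Section 12.2.3 makes the Wilcoxon test its lead analysis, or excludes every covariate but age.** It ranks no analysis, and it says the model is adjusted for age without saying that nothing else enters.
- **That a particular inflation of false positives follows.** Suppose a 10 to 15 point difference in percent female and a sex difference of 0.3 to 0.5 SD. The shift is 0.10 × 0.3 = 0.03 to 0.15 × 0.5 = 0.075 SD. With a normal test and standard error √(1/650 + 1/200) = 0.081, the rejection rate at a nominal 5% is about 7% to 15%; at the protocol's reduced sizes of 415 and 101 it is about 6% to 10%. Every input except the sample sizes is assumed. Larger figures can be produced by assuming an age gap of some years, but the design intends similar ages, and such a gap would affect only the crude test.

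**Conclusion.** The inconsistency is real and limited. For one score and one contrast, Section 12.2.2 requires age and sex, while Section 12.2.3 names age in a conditional model and otherwise adjusts for nothing. The Section 12.2.3 result can therefore be confounded by sex and can disagree with the Section 12.2.2 result. This rests on the protocol's text and on its own treatment of sex as a potential confounder of score components. It assumes no particular imbalance, and its size cannot be derived from the documents. Sample size and power are unaffected. It deserves correction because the correction is free and an adjusted comparison is already described elsewhere in the protocol.

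**What to change.** In Section 12.2.3:

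1. Change the logistic model's adjustment from age to age and sex, to agree with Section 12.2.2.
2. Label the Wilcoxon rank sum test as a crude comparison.
3. State that the inferential cohort comparison of PDAY is the age- and sex-adjusted model: the Section 12.2.2 GEE, or the logistic model if the scores are dichotomized.

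No new regression method is needed; a proportional-odds or rank-based regression would be a matter of preference. The cost is a few words, since age and sex are already collected.

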12.2.4 Sexually Transmitted Infections

Incidence of STIs, vaginal microbiota, LSIL, and HSIL, as well as the rate of regression of LSIL to normal cervical cytology, will be estimated under a Poisson distribution based on participant-years of follow-up. Only female participants with a first Pap smear indicative of normal cervical cytology and at least one subsequent Pap smear examination will be included when calculating incidence rates of LSIL and HSIL. If there are too few participants with incident LSIL or HSIL to accurately estimate the rate of regression, descriptive case data will be reported.

The incidence of each outcome will be compared between the YAPHIV and the YAPHEU comparison group using Poisson regression models. Factors associated with incidence of each outcome will be identified using Cox proportion hazards models and will adjust for important potential confounders including: CD4 count or %, viral load, ART use, CDC disease classification, contraceptive use, number of sexual partners, and smoking (for LSIL and HSIL).

12.2.5 Reproductive Health

The analysis of reproductive health outcomes will focus on estimating the prevalence and incidence of pregnancies (intended and unintended); pregnancy outcomes (live birth, induced abortion, spontaneous abortion, fetal death); the prevalence and incidence of menstrual irregularities; and the incidence of perinatal HIV transmission.

We will calculate prevalence estimates based on those with the specific outcome of interest divided by those with measurements for that outcome, along with 95% CIs. Incidence estimates will be calculated under a Poisson distribution based on participant-years of follow-up.

The prevalence of each outcome will be compared between the YAPHIV and the YAPHEU comparison group using chi-square tests as crude analyses and using logistic regression models for each separate outcome as a function of HIV status controlling for important demographic, and clinical and social factors (including but not limited to socioeconomic factors, partner characteristics, viral load, adherence, depression, and other behaviors).

Factors associated with prevalence of each outcome will be identified using logistic regression models. Factors associated with the incidence of each outcome will be identified using Cox-proportional hazards models. Factors associated with changes in reproductive health measures over time will be identified using GEE models, or mixed effect models when possible, to account for correlation between assessments on the same participant.

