2.0 OBJECTIVES AND HYPOTHESES

2.1 Primary Objectives

1. To identify infectious and non-infectious complications of HIV disease and toxicities resulting from long-term ART, including disease progression, immune dysfunction, viral resistance, end-organ disease, and mortality.
2. To define the impact of HIV infection and ART on the long-term clinical outcomes in YAPHIV, including:
 - Metabolic abnormalities and risk factors for CVD, including derangements in glucose and lipid metabolism, blood pressure, and body composition.
 - STIs (*C. trachomatis*, *Neisseria (N.) gonorrhoeae*, *T. vaginalis*, syphilis, HPV, genital and anal warts, and HSV) among males and females, and cervical HPV-associated pre-cancers and cancers and other vaginal microbiota, and pelvic inflammatory disease among females.
 - Reproductive health, fertility, and pregnancy outcomes including perinatal transmission of HIV.
3. To define the impact of perinatal HIV infection, its concomitant risk factors, and ART on long-term neurocognitive and behavioral health outcomes, including:

- Mental health (both psychiatric disorders and emotional/behavioral functioning) and neurocognitive functioning.
- Health care behaviors, including adherence to ART, participation in health care services, and transition to adult clinical care.
- Risk behaviors, including sexual behavior and substance use (alcohol, tobacco, vaping, and licit and illicit drugs).
- Hearing and language impairments.
- Independent living skills, vocational and educational achievement, life satisfaction, resilience, and health-related QoL.

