2.2.5 Reproductive Health

Specific Aims:

Among WLPHIV and WLPHEU:

- To describe the use of pregnancy prevention methods and their association with pregnancy and STI outcomes.
- To determine incidence of and factors associated with pregnancy intention.
- To examine pregnancy outcomes and factors associated with these outcomes.
- To identify rates of menstrual irregularities and risk factors for menstrual irregularity, including stress, hormonal disturbances, HIV-related health, and ART use.
- To determine the incidence of perinatal transmission of HIV.

Among WLPHIV, in comparison to women living with non-perinatally acquired HIV from the Health Outcomes around Pregnancy and Exposure to HIV/ARVs (HOPE) study:

- To evaluate individual, mental health, and interpersonal factors associated with unintended pregnancy, contraceptive discontinuation or non-use, discordant family planning behaviors and desires, and incident STIs.
- To compare factors associated with unintended pregnancy, contraceptive discontinuation or non-use, discordant family planning behaviors and desires, and incident STIs by mode of HIV acquisition (PHIV vs. non-PHIV).

Hypotheses:

- The majority of WLPHIV who use pregnancy prevention will choose long-acting contraceptives. These methods will be superior to combined oral contraceptive pill in preventing pregnancies; however, they will be linked to lack of condom use and higher STI rates.
- Predictors of pregnancy intention will be similar for WLPHIV and WLPHEU and will include older age and perceived close relationship to partner.
- Young WLPHIV who are not on contraceptives will be more likely than young WLPHEU to have anovulatory cycles (defined as having cycles < 21 and > 35 days). Irregular cycles will be affected by stress, depression, BMI, and substance use, and for WLPHIV, CD4 cell count and ART adherence.
- Young WLPHIV will have fewer pregnancies than WLPHEU after adjusting for BMI, STI history, and substance use. Vaginal dysbiosis will be associated with fewer pregnancies.
- Young pregnant WLPHIV will have higher spontaneous abortion rates than WLPHEU after adjusting for substance use. Vaginal dysbiosis will play a role in this increased rate of spontaneous abortion.
- The rate of perinatal transmission of HIV will be low.

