3.1 Study Population

Participants in this study will be YAPHIV and YAPHEU at or beyond their 18th birthday who were born to mothers living with HIV during their pregnancy. Eligible participants will be recruited from PHACS sites and will include those with a well-documented history of their major medical events history, and for participants with HIV only, HIV infection status, viral load and CD4 cell count history, and ART since early childhood.

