4.7 Co-Enrollment Guidelines

Enrollment of AMP Up participants in other studies (with or without similar goals/data collection as AMP Up) is at the discretion of clinical site principal investigators. However, they must take into account any issues that enrollment in the additional study may require, and which may compromise the site's ability to fulfill the requirements of PHACS.

Children born to female YAPHIV AMP Up participants are encouraged to be enrolled along with their mothers in the SMARTT dynamic cohort.

Participants who indicate they would like to be contacted for studies opening in the future will provide their contact information to the clinical site. Each site will maintain this information and, in the event a participant changes their mind and no longer wishes to be contacted, the clinical site will track these requests and update their documentation accordingly.

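### Perinatal HIV transmission is to be estimated per participant-year of adult follow-up, which mixes birth rate, per-infant risk and ascertainment; the denominator should be exposed infants of known HIV status.

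*Protocol*

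**What the plan says.** Section 2.1 places the outcome in Primary Objective 2: "Reproductive health, fertility, and pregnancy outcomes including perinatal transmission of HIV". Section 2.2.5 makes it a specific aim, "To determine the incidence of perinatal transmission of HIV", and attaches a hypothesis without a threshold: "The rate of perinatal transmission of HIV will be low".

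Section 12.2.5 names pregnancies and menstrual irregularities for both prevalence and incidence, but this outcome for incidence alone: "and the incidence of perinatal HIV transmission". Its incidence rule is a single sentence, "Incidence estimates will be calculated under a Poisson distribution based on participant-years of follow-up". The section's only formula that divides by people measured is for prevalence ("prevalence estimates based on those with the specific outcome of interest divided by those with measurements for that outcome"), and prevalence is not assigned to transmission.

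On whose years are counted, Section 3.1 says: "Participants in this study will be YAPHIV and YAPHEU at or beyond their 18th birthday". Infants are not AMP Up participants. Section 4.7 gives one route to them: "Children born to female YAPHIV AMP Up participants are encouraged to be enrolled along with their mothers in the SMARTT dynamic cohort". The Study Abstract lists reproductive history among the items abstracted annually, and Section 9.1 lists pregnancy circumstances among the survey topics. Neither says whether the HIV status of a child is recorded.

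**The concern.** An infant can acquire HIV perinatally only if the mother is living with HIV. The natural unit is the exposed infant, and the natural measure is the proportion infected. A year in which a woman has no exposed pregnancy or infant is not time at risk, yet under the stated rule it enters the denominator.

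The protocol does define the population at risk for other incidence outcomes. Section 12.2.2 uses person-time of people initially free of the metabolic risk factor. Section 12.2.4 requires a normal first Pap smear and at least one later one for LSIL and HSIL. Section 12.2.5 has no such restriction.

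At stake is whether the estimate can answer its own hypothesis. A low rate per participant-year could come from few births, from few infants of known status, or from low transmission, and the figure alone does not show which. The outcome concerns the safety of third parties, so a misleadingly reassuring figure matters.

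**Working it through.** The protocol gives no rate, sample size or precision for this outcome, so there is no stated figure to reproduce. The check shows how the planned measure behaves.

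**Inputs**
- Pregnancy rate of 7.4 per 100 person-years and a live-birth share of 36%, from a study of women with sexually acquired HIV cited in Section 1.1.6. Used for illustration only.
- A second live-birth share of 60%: assumption, used only to change the birth rate.
- Risk per live-born infant *r*: assumption, 1%, with a range of 0.5% to 2%.
- Share of infants with known HIV status *k*: assumption, 100% or 50%.
- Follow-up: assumption, 325 women (half of the 650 in Section 3.2) for 6 years = 1,950 participant-years.

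**Step 1: what the rate measures.** Transmissions per participant-year = *b* × *r* × *k*, where *b* is live births per participant-year.

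*b* = 7.4 × 0.36 = 2.66 per 100 participant-years, or 7.4 × 0.60 = 4.44 per 100.

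| Births per 100 participant-years | *r* | *k* | Transmissions per 1,000 participant-years |
|---|---|---|---|
| 2.66 | 1% | 100% | 0.27 |
| 4.44 | 1% | 100% | 0.44 |
| 2.66 | 1% | 50% | 0.13 |
| 2.66 | 2% | 50% | 0.27 |

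The first two rows have the same risk and full ascertainment, but the rate differs by 4.44 / 2.66 = 1.67. The first and last rows give the same rate although the risk differs twofold. For *r* from 0.5% to 2% with full ascertainment, the rate runs from 0.13 to 0.53 at the lower birth rate and from 0.22 to 0.89 at the higher one.

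**Step 2: precision with no transmissions.** The upper limits of two-sided 95% exact intervals are:
- Per participant-year (Poisson): −ln(0.025) / 1,950 = 3.689 / 1,950 = 1.89 per 1,000.
- Per infant (binomial): 1 − 0.025^(1/*n*), where *n* is the expected number of infants of known status.

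| Expected births | Known status | *n* | Upper limit per infant | Upper limit per 1,000 participant-years |
|---|---|---|---|---|
| 1,950 × 0.02664 = 51.9 | 100% | 51.9 | 6.9% | 1.89 |
| 51.9 | 50% | 26.0 | 13.2% | 1.89 |
| 1,950 × 0.0444 = 86.6 | 100% | 86.6 | 4.2% | 1.89 |
| 86.6 | 50% | 43.3 | 8.2% | 1.89 |

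The evidence about transmission varies about threefold across these rows (13.2 / 4.2 = 3.1), while the planned limit does not move.

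**The case against.** The best defence is that the sentence in Section 12.2.5 is generic. It also serves pregnancies and menstrual irregularities, where participant-years are sensible, and a denominator specific to one outcome could be set in a statistical analysis plan that is not shown. That lowers the severity. It does not remove the point, because the text assigns transmission to incidence and fixes the denominator for every incidence in the section, with no exception.

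Several stronger readings are tempting, and the document does not support them:
- *No infant HIV status is collected.* The schedules work by category. Reproductive-history abstraction and SMARTT co-enrolment are possible routes, and pregnancy outcomes, plainly meant for analysis, also have no schedule row of their own. What can be said is that the source is not stated.
- *Infants of unknown status are treated as uninfected.* Section 12.2.5 gives no rule for them. The planned rate depends on ascertainment, but no such coding is prescribed.
- *The hypothesis of a low rate is confirmed automatically.* No threshold or test is attached, and any recorded transmission still enters the numerator.
- *The planned rate understates risk many-fold.* Setting a figure per person-year against a figure per birth only changes the unit.
- *The two cohorts will show a twofold artefact.* Section 1.1.6 also cites 15.2 pregnancies per 100 person-years, but in HIV-uninfected women, so it cannot forecast transmissions. The cohort comparison specified in Section 12.2.5 is of prevalence.
- *Naming women with PHEU in the aim is a mistake.* Under Section 8.1, a YAPHEU participant who acquires HIV is asked to stay on study and could have an exposed infant.

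**Conclusion.** The point holds for the denominator. Followed as written, Section 12.2.5 yields a rate that depends on transmission risk but cannot be separated from birth rate and ascertainment, and whose interval does not reflect the number of exposed infants. That follows from the definition and needs no assumption. The sizes shown rest on an assumed per-infant risk, ascertainment share, follow-up time and second live-birth share, and on a pregnancy rate and live-birth share from a different population. They illustrate the behaviour and do not forecast this cohort's result. The unstated source of infant status is a secondary gap. The matter should be corrected because the outcome is part of a primary objective, but it is confined to one outcome and is easily repaired.

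**What to change.** In Section 12.2.5, take perinatal transmission out of the participant-year rule and define it as:
- **Numerator:** infants with perinatally acquired HIV.
- **Denominator:** live-born infants of known HIV status whose mothers were living with HIV at the time of the pregnancy, including infants of any YAPHEU participant who has acquired HIV.
- **Interval:** exact binomial, with allowance for siblings, for example by repeating the estimate with one infant per mother.
- **Completeness:** report the number of exposed live-born infants of unknown status beside the estimate.
- **Source:** SMARTT linkage where the child is co-enrolled; otherwise the mother's reproductive-history abstraction or survey, where the information is available. Section 8.2 has participants with cognitive impairment who are surveyed by interview skip the reproductive questions, so the survey cannot be the only fallback.

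Participant-years can stay for pregnancies and menstrual irregularities. The cost is a wording change, a wider and less favourable-looking interval, and possibly a small abstraction burden. Whether a mother's record holds the child's status is not stated, so some infants may remain unknown.
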